SUMMARY

Rationale: Infertility is a worldwide problem and about 10%-15% of all couples will be affected by the inability to have children. In approximately 50% of infertile couples a male factor is involved. In the past decade, the role of oxidative stress on sperm has been researched thoroughly and found to be the problem in 30% to 80% of male infertility cases. Impryl® is a nutritional supplement which works on the metabolic system and regulation of oxidative stress by activating the 1-Carbon cycle and therefore recycling of homocysteine.

Objective: To determine the effectiveness of nutritional supplement Impryl® in men of infertile couples on ongoing pregnancy rate, with or without assisted reproduction technology (ART).

Study design: Multicentre, randomised double blind placebo controlled clinical trial/superiority study.

Study population: All participants in this study are male adults, age 18-50 years, part of a couple that is diagnosed with infertility, regardless the outcome of semen analysis. The couple will either start or is already started with fertility treatment, i.e. expectative management (EM, duration 6 months), intra-uterine insemination (IUI) with or without ovarian stimulation (mild ovarian hyperstimulation (MOH) or ovulation induction (OI)), either in vitro fertilization (IVF) or intracytoplasmic sperm injection (ICSI) treatment.

Intervention: Impryl® or placebo, with identical appearance one tablet each day for a total duration of maximal 6 months. Patients can start directly with fertility treatment and/or to conceive.

Main study parameters/endpoints: The primary outcome is the number of ongoing pregnancies confirmed by ultrasound at ≥ 10 -12 weeks, and conceived in the time window between randomization up to and including month 6 of intervention use. Secondary outcomes are change in semen parameters between baseline and 3 months intervention in IUI/IVF/ICSI group, based on (pre-wash) total motile sperm count (TMSC), leading to a different fertility treatment categorisation. Furthermore the number of pregnancies conceived in the optimal intervention time window, the overall number of pregnancies, time to pregnancy, embryo fertilization rate in IVF/ICSI, embryo-utilization rate in IVF/ICSI, number of miscarriages and live birth rate are documented within the study period of 15 months. The occurrence of adverse events will be reported.

Nature and extent of the burden and risks associated with participation, benefit and group relatedness: Couples with infertility will receive standard fertility treatment, i.e. EM or ART. The risks and burden of participating in the trial are small. After a complete diagnostic work-up for infertility, the males will be randomised for use of either Impryl® or placebo. Impryl® is a food supplement already free available throughout Europe, online in the

Netherlands. Males need to take study medication (one tablet each day) for a maximum of 6 months in total. For this study, we want to measure improvement of semen parameters after at least 3 months use of study medication. Performing a pre-wash TMS is standard procedure at most sites when semen is used for IUI or IVF/ICSI. However, in couples with EM performing a TMS after 3 months is not standard care. We decided not to perform a semen analysis in the EM group due to the fact that improvement in fertility treatment from expectative management is not possible. Participants are required to collect study medication directly at their local hospital or at Radboudumc. At the start of taking study medication the couple is asked to fill in a questionnaire about their baseline characteristics. To assess lifestyle changes during intervention and amount of used study medication, every male will be asked each month (6 times in total) to fill in an online questionnaire, these monthly questionnaires stop when a pregnancy has been reached. Every couple will receive a final questionnaire, 15 months after inclusion, about the outcome of fertility treatment and occurrence of pregnancy. If a woman is pregnant, standard care is an ultrasound around 10-12 weeks to estimate the due date. To limit the amount of extra site visits to zero, we decided that this 'due date' ultrasound at 10-12 weeks of pregnancy is enough for determining the primary outcome. The ultrasound can be made in the midwife practice. Information about the outcome of this ultrasound is reported in the 15-months questionnaire. In conclusion, the burden and risks associated with participation in this trial can be considered negligible.

INTRODUCTION AND RATIONALE

[figure not shown]
Infertility is a worldwide problem and about 10%-15% of all couples will be affected by the inability to have children.(1, 2) In approximately 50% of infertile couples a male factor is involved.(3) Male infertility is of multifactorial origin. In the past decade, the role of oxidative stress on sperm has been researched thoroughly and found to be the problem in 30% to 80% of male infertility cases. (4-8)

Reactive oxygen species (ROS) are products of normal cellular metabolism. However, oxidative stress occurs when the ROS production overwhelms the semen's natural antioxidant defenses and causes cellular damage.(9) Increased oxidative stress is due to environmental and lifestyle factors such as smoking, stress, obesity and nutrition. ROS act by directly altering the sperm DNA and by damaging the sperm membrane and therefore affecting the sperm motility and ability of the spermatozoa to break down the oocyte membrane during fertilization. Men with sperm DNA damage can still have normal seminal parameters, however having a poor chance of natural conception.(10) Antioxidants can provide protection against oxidative stress by neutralizing the free oxygen radicals. Examples of antioxidants already present within seminal plasma are ascorbic acid (Vitamin C), α -tocopherol (Vitamin E), glutathione, amino acids (taurine, hypotaurine), albumin, carnitine, carotenoids, flavenoids, urate and prostasomes. Despite the common association between male infertility and oxidative damage, men are rarely treated or screened for oxidative stress. The latter because of the cost and complexity of testing for DNA damage. A recent Cochrane review suggested that antioxidant supplementation in male infertility might improve the outcomes in assisted reproductive technologies (ART). However, the evidence was rated as low and other clinical studies showed contradictory results with even a negative effect of high doses of antioxidants due to reductive stress as a rebound effect.(11)The clinical data on the effect of oral antioxidants in female infertility are even weaker, which is suggested to be the result of heterogeneity in study designs.(12) Alternatives to the straight oral antioxidants were therefore explored. A suitable alternative is to support the natural antioxidant defenses that are predicted to act within the modulation of the natural cellular homeostasis without generating rebound effects. Studies showed a positive effect of a nutritional supplement Condensyl®, the precursor of Impryl®, supporting DNA methylation patterns.(13, 14) Homocysteine is the end-product of the 1-Carbon cycle (feeding DNA methylation) as well the starting substrate for GSH (the tripeptide glutathione) de novo biosynthesis (feeding reducing power to the antioxidant defenses). Homocysteine is in turn an inhibitor of the methylation process and a powerful pro-oxidant. It has a negative effect on spermatogenesis quality and its concentration in the ejaculate is inversely correlated with fertility outcome.(15, 16) Dattilo et al stated that the ideal supplement should work by favoring homocysteine recycling by restoring the efficiency of the 1-Carbon cycle, therefore ensuring the availability of activated methyl groups for DNA methylation and by supporting GSH synthesis, feeding the intracellular antioxidant system. (17) In the non-randomized pilot studies with Condensyl® there was a significant decline of DNA fragmentation index leading to an improvement of the clinical pregnancy rate. However, the quality of these studies for the impact on pregnancy rate is rather low due to the non-

randomized nature and in the study of Dattilo et al. performed in 2014 there was no control group.(13, 15)

Impryl® is a nutritional supplement mainly consisting of vitamin B, which works on the metabolic system by activating the 1-Carbon cycle and recycling of homocysteine without the use of any direct strong antioxidants. Compared to Condensyl®, Impryl has the added advantage of the activated forms of folate (methylfolate) and B12 (methylcobalamine) to neutralize the effect of the enzyme variants and is therefore predicted to be more effective. The exact mechanism of action of Impryl® is shown in figure 1, Impryl® provides substrates and co-factors in the GSH synthesis to normalize the redox homeostasis.

Figure 1. Working mechanism of Impryl®

In conclusion, it is well known that assisted reproduction technologies are expensive and that male infertility is being responsible for approximately 30% of problems with conception and to be a contributory factor in 50%.(18, 19) The medical and non-medical cost per IVF treatment in the Netherlands is estimated to be between 2.885 and 5.259 euro (€) when being expressed in the year 2015 euro by means of the consumer price index (<http://statline.cbs.nl>).(20, 21) The medical and non-medical costs per non-stimulated and stimulated IUI cycle are respectively 497€ and 1123€ for the year 2015.(22) Therefore, substantial cost savings would be made if the use of relatively inexpensive nutritional supplements would lead to a higher ongoing pregnancy rate, a shorter time to pregnancy or to the use of less expensive, less invasive reproductive techniques.

OBJECTIVES

Primary Objective: To test the hypothesis that the number of ongoing pregnancies (i.e. ≥ 10 -12 weeks of gestation) , conceived in the time window between randomization up to and including month 6 of intervention use, will be different in couples treated with Impryl® for infertility, compared to couples with a placebo.

Secondary Objectives:

Number of pregnancies conceived in the optimal intervention time window, i.e. between start of month 4 till the end of month 6. Overall pregnancy rate. Time to pregnancy defined as both the time between a) randomization and reaching ongoing pregnancy, and as b) start of fertility treatment during the study (EM, IUI, IVF/ICSI) and reaching ongoing pregnancy. Change in semen parameters leading to different fertility treatment categorisation (for more details see page 26) between baseline and 3 months intervention, based on pre-wash total motile sperm count (TMSC) from the subpopulation from Radboudumc and sites that deliver a pre-wash TMSC before IUI/IVF/ICSI. Improvement between Impryl® and control group in fertilization rate and embryo-utilization rate in IVF/ICSI group. Fertilization rate is defined as the percentage of oocytes with 0 PN or ≥ 2 PN after insemination (IVF) or injection (ICSI). Abnormal fertilization such as 3PN will be recorded, in case this percentage differs or increases in the study group. The embryo-utilization rate (EUR) is defined as the number of high quality embryos obtained, embryo's used at transfer plus the number of embryos frozen, divided by the number of zygotes obtained in a cycle. Due to the differences in embryo evaluation and embryo selection criteria for cryopreservation, we decided to measure the relative increase in fertilization and utilization rate observed for each clinic.. Number of miscarriages defined as a non-vital intra-uterine pregnancy before 16 weeks of gestation. Live birth rate defined as beyond 24 weeks of gestation, the birth of a living child. Live births (beyond 24 weeks, defined as the birth of a living child) will be reported within follow-up time of 15 months. Furthermore the following adverse events will be reported: gastro-intestinal problems such as reflux, obstipation, diarrhea, nausea or vomiting, furthermore loss of appetite, headache, dizziness, pruritus or skin rash.

STUDY DESIGN

A multicentre randomised, double blind placebo controlled, clinical trial for Impryl® administration will be performed in the Department of Gynaecology and/or Reproductive Medicine in both academic and non-academic hospitals in The Netherlands.

The 16 centers participating in the study:

| Hospital | Principal investigator |
|---|--------------------------------|
| Radboudumc, Nijmegen | [name] |
| Slingeland Ziekenhuis, Doetinchem | [name] |
| Canisius-Wilhelmina Ziekenhuis, Nijmegen | [name] |
| Jeroen Bosch Ziekenhuis, Den Bosch | [name] |
| Elisabeth-TweeSteden, Tilburg | [name] |
| Maasziekenhuis Pantein, Boxmeer | [name] |
| Bernhoven Ziekenhuis, Uden | [name] |
| Maxima Medisch Centrum, Veldhoven | [name] |
| Maastricht UMC+, Maastricht | [name] |
| Gelre ziekenhuizen, Apeldoorn | [name] |
| Nij Geertgen, Elsendorp | [name] |
| Rijnstate, Arnhem | [name] |
| Medisch Centrum Kinderwens, Leiderdorp | [name] |
| Nij Barrahûs | [name] |
| Fertiliteitscentrum Voorburg | [name] |
| Catharina Ziekenhuis Eindhoven | [name] |
| Bravis Ziekenhuis locaties Roosendaal en Bergen op zoom | [name] and [name] |

The duration of the study will be approximately 45 months. A run-in period of 6 months is needed for the study set up. The inclusion period will be 24 months. A period of 15 months is needed for follow-up data collection and report of results. We anticipate on a 50% participation rate; the study will be completed in 3.5 - 4 years. Our study design is summarized in figure 2 and a time line is shown in figure 3.

Figure 2. Flow chart study design

[figure not shown]
[figure not shown]

Figure 3. Time line study (T in months)

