1.3 Sample size calculation

The overall success rate (number of ongoing pregnancies, not specified per cycle number) in IVF and ICSI in the Netherlands was respectively 19.8% and 21.5% per cycle in 2015.(23) The cumulative number of ongoing pregnancies in IUI is estimated to be around 5 to 13% per cycle, around 18% after three cycles and 20-30% after six cycles. (24-26) Based on our Radboudumc data, the ongoing pregnancy rate in EM is estimated around 20% after 6 months.

A Cochrane review ‘antioxidants for male subfertility’ estimated the increase in clinical pregnancy rates after use of antioxidants with an Odds Ratio (OR) of 3.43 (95% CI 1.92 to 6.11, $P < 0.0001$, 7 RCTs, 522 men, $I^2 = 0\%$, low quality evidence). (27) However, this concerns low quality evidence, and the included population in this Cochrane review was couples with male factor subfertility, whereas in our study we also include couples with unexplained infertility. Therefore, we assumed a more conservative OR of 1.5. Assuming a 20% ongoing pregnancy rate in the placebo group, this reflects in an expected pregnancy rate of 27.3% in the Impryl® group

The study is designed as a superiority study. Based on the above mentioned data, we expect a 7.3% increase in ongoing pregnancy number when men are treated with Impryl® compared to placebo. However, after randomization patients can directly start with both intervention and achieving a pregnancy, either spontaneously or with fertility treatment. In these first months the effect of the intervention is expected to be suboptimal due to the duration of the spermatogenesis (72 days before whole renewal). Therefore we adjusted the expected increase of 7.3% to a more realistic effect of 6.5%. We assume an equal increase in all fertility groups (meaning EM, IUI and IVF/ICSI) from 20% to 26.5%.

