The ratio between the 3 fertility treatment groups (EM 1: IUI 3: IVF/ICSI 2) is based on the number of new patients treated at Radboudumc and the sites each year. To test the effect of Impryl on the probability of ongoing pregnancy, a sample size of 600 men per treatment group (1200 in total) is needed, assuming differences in ongoing pregnancy rates of 6.5% and an expected ongoing pregnancy rate of 20% in the placebo group, with a two-sided alpha of 5% and a beta of 24% (i.e. 76% power). As we expect the number of participants lost to follow up to be minimal. We will allocate 600 patients in both intervention and control arm. Figure 1 shows the distribution of the number of participants for the 3 different types of fertility treatment (EM, IUI and IVF/ICSI).

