Semen analysis will be performed two times: once during diagnostic work-up (standard care, analysis according to WHO criteria(28) and once more after approximately 3 months of using study medication (ie. after three months of IUI treatment or IVF/ICSI). At several sites, a pre-wash TMSC is standard care when performing an insemination (IUI group) and will be performed on the semen produced for IVF/ICSI as part of routine measurement before procedure. Because semen analysis performed at the time of treatment cannot be fully performed according to the WHO criteria, we will categorize the TMSC quality according to the allocated treatment category. This means, that the TMSC (evaluated at the start of treatment and after 3 months) will be analyzed according to changes in allocated treatment category based on the NVOG guideline(29). The criteria for treatment are given in the table below. A change in treatment category means an improvement in sperm quality that would allow a lower treatment category (e.g, from ICSI to IVF)

| TMSC outcome ($\times 10^6$) | WHO Diagnostic category | NVOG Treatment category |
|--------------------------------|-------------------------|---|
| > 10 | Normospermia | EM |
| 3 -10 | Mild OAT | IUI |
| 1-3 | OAT | IVF/ICSI (if after wash VCM is <0,5) |
| <1 | Extreme OAT/Azoospermia | ICSI |

OAT = oligo-astheno-teratozoospermia.

* Or IVF depending on the prediction model of Hunault and other clinical characteristics

We decided not to perform a semen analysis in the EM group due to the fact that they already have normal semen parameters at intake and the burden of an extra visit is high.

Fertilization and embryo-utilization rate

In IVF/ICSI patients fertilization rate and embryo-utilization rate are standard reported by every IVF-laboratory. Fertilization rate is the percentage of oocytes with ≥ 2 PN after insemination (IVF) or injection (ICSI). The embryo-utilization rate (EUR) is defined as the number of high quality embryos obtained, embryo's used at transfer plus the number of embryos frozen, divided by the number of zygotes obtained in a cycle. Due to the differences in embryo evaluation and embryo selection criteria for cryopreservation, we decided to measure the relative increase in fertilization and utilization rate observed for each clinic.

Transvaginal ultrasonography

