7. STATISTICAL ANALYSIS

All data will be analyzed on an intention-to-treat basis. Data of patients who are lost to follow-up, will be included in their randomised group

will be included in their randomized group:

- Patients who are lost to follow-up during the treatment period are considered not to have achieved a pregnancy.
- Patients, who are lost to follow-up right after achieving a pregnancy of less than 8 weeks of gestation, are considered not to have achieved an ongoing pregnancy
- Patients, who are lost to follow-up right after achieving a pregnancy of 8 or more weeks of gestation, are considered to have achieved an ongoing pregnancy.

In addition, a per-protocol analysis will be performed for the primary outcome and the secondary outcomes overall pregnancy number, time to pregnancy, number of miscarriages and live birth rate.

Descriptive statistics will be calculated to check for major dissimilarities between study groups with respect to baseline information. Baseline data will be described quantitatively. For continuous variables, we will examine the distribution of the observations, and if normally distributed we will summarise them as means with standard deviations (SDs). If they are not normally distributed, then medians and inter-quartile ranges (IQRs) will be reported. For dichotomous data, we will provide counts and proportions.

The primary outcome variable 'ongoing pregnancy' will be assessed as follows. The ongoing pregnancy percentages as observed in the trial will be presented for both treatment arms, overall, and separately for the three strata (i.e. EM, IUI, IVF/ICSI). In order to adjust for possible imbalances between the treatment groups, the pregnancy percentages and differences in pregnancy percentages between the experimental and control group, and the corresponding 95% confidence intervals will be estimated using a fixed effects binomial model with an identity link, including intervention, fertility treatment, centre and female age (centered). If this model does not converge, a logit link will be used.

Time to ongoing pregnancy will be evaluated by the Kaplan-Meier approach; differences between the two arms will be tested with the log-rank test. Similar analyses will be conducted per stratum (EM, IUI or IVF/ICSI). The other secondary outcomes (overall pregnancy number, number of miscarriages, live birth rate, fertilization rate, embryo-utilization rate) will be evaluated similarly to the primary outcome. Changes in semen

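### The fertilization rate cannot separate normal from abnormal fertilization: all three definitions count 3PN oocytes, and two also count 0 PN

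*Combined protocol and SAP*

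**What the plan says.** The combined protocol and SAP defines the fertilization rate in three places.

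- Secondary Objectives and section 5.1.2, in identical words: "Fertilization rate is defined as the percentage of oocytes with 0 PN or ≥ 2 PN after insemination (IVF) or injection (ICSI").
- Section 5.3, under fertilization and embryo-utilization rate: "Fertilization rate is the percentage of oocytes with ≥ 2 PN after insemination (IVF) or injection (ICSI").

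The Secondary Objectives and section 5.1.2 then add: "Abnormal fertilization such as 3PN will be recorded, in case this percentage differs or increases in the study group". Section 5.3 has no such sentence.

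The aim is stated as "Improvement between Impryl® and control group in fertilization rate and embryo-utilization rate in IVF/ICSI group", so a higher rate is the favourable direction. Section 7 says only that the outcomes ending in "fertilization rate, embryo-utilization rate) will be evaluated similarly to the primary outcome". It lists no analysis of 3PN.

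**The concern.** A numerator open at the top end takes in 3PN, which the plan itself labels abnormal and foresees might increase in the study group. An event called abnormal therefore counts towards an outcome on which a higher value is the stated aim. The rate could credit extra abnormal fertilization to the supplement, or stay flat while normal fertilization falls.

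The definitions also disagree with each other. Two of them place 0 PN oocytes in the numerator and the third does not. Adopting the section 5.3 wording would settle the 0 PN conflict but leave 3PN in the count, so each problem needs attention even though one change of wording can cure both.

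**Working it through.** **Inputs.** The three definitions above. The document gives no expected fertilization rate and no share for any pronuclear class, so there is no stated figure to reproduce. All shares below are assumptions chosen to show direction.

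**Formulas.** Let n0, n1, n2 and n3 be the oocytes with 0, 1, 2 and ≥3 PN, and N = n0 + n1 + n2 + n3 (this assumes every oocyte falls in one class).

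- A, Secondary Objectives and section 5.1.2: (n0 + n2 + n3) / N, which equals 1 − n1/N
- B, section 5.3: (n2 + n3) / N
- C, exactly 2 PN: n2 / N

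A depends only on the 1PN share. In both A and B, an oocyte moving into ≥3 PN adds one to the numerator and removes at most one from it. Neither rate can fall because 3PN rises.

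**One group, assumed 100 oocytes: 25 with 0 PN, 5 with 1PN, 65 with 2PN, 5 with 3PN.**

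| Case | A | B | C | 3PN |
|---|---|---|---|---|
| Base | 25+65+5 = 95% | 65+5 = 70% | 65% | 5% |
| 5 move from 1PN to 3PN | 25+65+10 = 100% | 65+10 = 75% | 65% | 10% |
| 5 move from 0 PN to 3PN | 20+65+10 = 95% | 65+10 = 75% | 65% | 10% |
| 5 move from 2PN to 3PN | 25+60+10 = 95% | 60+10 = 70% | 60% | 10% |
| 10 move from 0 PN to 2PN | 15+75+5 = 95% | 75+5 = 80% | 75% | 5% |

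The second and third rows show B rising by 5 points with no extra normal fertilization; A rises only in the second. The fourth row shows a 5-point loss of normal fertilization that neither A nor B registers. The last row shows a true 10-point gain that A misses entirely, because it already counted the 0 PN oocytes.

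**Two arms, definition B, assumed rates (control v Impryl).**

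- Spurious gain: 2PN 60% v 60%, 3PN 4% v 8%. Rate 60+4 = 64% v 60+8 = 68%, a difference of 4 points with 2PN unchanged.
- Hidden gain: 2PN 60% v 63%, 3PN 8% v 5%. Rate 60+8 = 68% v 63+5 = 68%, a difference of 0 although normal fertilization is 3 points higher.

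The first result carries over to definition A only if the 4 extra points of 3PN come from 1PN. If they come from 0 PN, the difference under A is 0. The second carries over to A if the 0 PN share is the same in both arms.

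**Reach.** With the planned 1:3:2 ratio of EM, IUI and IVF/ICSI in section 1.3, the IVF/ICSI stratum is about 1200 × 2/6 = 400 men.

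**The case against.** The strongest reply is that the plan already guards against this. 3PN is to be recorded, and the clause beginning with in case reads naturally as the reason for recording it, not as a condition on it. The trial is double blind, so blinded staff could not limit recording to one arm. A difference in 3PN could therefore be seen. That stands: the 3PN data should exist in both arms. What is missing is a rule that keeps 3PN out of the efficacy rate and a named comparison of 3PN by arm.

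It can also be said that ≥2 PN is a deliberate measure of total fertilization, or simply what laboratories report. The plan does not say that total fertilization is intended, and counting 0 PN in two of the three definitions does not fit that reading.

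The consequence is also limited. This is one of several secondary outcomes in one stratum, and embryo utilization, ongoing pregnancy and live birth are measured downstream and would help in interpreting an isolated fertilization gain. That bears on how much the point matters, not on whether the definition is sound.

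A reader might infer that any rise in 3PN would appear as an improvement, point for point. The definitions do not support that. When the extra 3PN oocytes come from 2PN, or from 0 PN under the Secondary Objectives and section 5.1.2, the rate does not move.

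**Conclusion.** Wrong as written. The fertilization rate mixes normal fertilization with an outcome the plan calls abnormal, and two of its three definitions also count 0 PN, contradicting the third. Depending on which class the extra 3PN oocytes come from, the rate either rises or conceals a loss of 2PN; it never falls.

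The direction follows from the definitions alone, given that each oocyte is assigned to one class. The size cannot be fixed from the document: the 4-point and 3-point illustrations, like the 100-oocyte table, rest on assumed pronuclear rates. Nothing in the document shows that Impryl raises 3PN, and the point does not need it to. It concerns a secondary outcome in the IVF/ICSI stratum; the primary outcome and the sample size are unaffected.

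**What to change.** 1. In the Secondary Objectives, section 5.1.2 and section 5.3, use one definition: oocytes with exactly 2 PN divided by oocytes inseminated (IVF) or injected (ICSI).
2. Record counts of 0, 1, 2 and ≥3 PN for each cycle in both arms. Subtracting 3PN from the present rate is not enough under the Secondary Objectives and section 5.1.2, because that leaves 0 PN plus 2PN.
3. In section 7, report the ≥3 PN proportion by arm, with the between-arm difference and its 95% CI.
4. If laboratories' routine ≥2 PN rate is of interest, keep it as a supplementary result under its own name.

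The cost is a wording change in four places and the recording of four counts per cycle; section 5.3 says IVF laboratories already report fertilization rate as standard, so the added work should be small. The downsides are that the trial's rate may differ from a laboratory's routine figure, and that there is one more descriptive comparison.
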